- 13) To be completed electronically by patient, in clinic, prior to any blood draw, physical exam, or vital sign measurements.
- 14) See [Appendix 5](#) for biopsy assessments. The post-treatment endoscopy (EGD) and biopsy assessments will be performed on Day 169 (± 3) or 28 (± 3) days after last dose of study drug if ET. If the Day 141 infusion occurs out of window, the EGD should occur 28 (± 3) days from the date of Day 141. Post-treatment EGD biopsy results will be blinded to the site.
- 15) Blood for baseline Chemistry, including hCG and FSH, will be collected during the screening period. Only patients of childbearing potential and post-menopausal women are required to have hCG and FSH testing completed.
- 16) Blood for Serology testing will be collected during screening and will include HBsAg, hepatitis C antibody, anti-HBc, and HIV, as well as *Strongyloides stercoralis*.
- 17) Blood samples for Total Serum IgE will be collected during screening and on Day 176 or 35 (± 3) days after last dose of study drug, if ET.
- 18) Stratification based on TSS of <28 or ≥ 28 and whether patient is EoD-only will occur. Randomization and stratification will be conducted through the IRT system.
- 19) Premedication with 60 mg oral prednisone or approved alternative is required 12–24 hours prior to first infusion. Premedication may be administered prior to subsequent infusions at the Investigator's discretion, but only with written Medical Monitor approval.
- 20) Study drug will be administered as a single peripheral IV infusion over at least 4 hours for Dose 1 and at least 3 hours for Dose 2. Doses 3–6 should occur over at least 2 hours, depending on prior infusion tolerability. Please refer to the Pharmacy Manual.
- 21) Blood for CBC with differential, including absolute blood eosinophil count, will be obtained just prior to each infusion, 1 hour (± 15 minutes) after the end of each infusion as well as during the screening period, and on Days (± 3) 8, 15, 169, 176, 197, and 225 or 35, 56, and 84 (± 3) days after last dose if ET. All differential blood counts from Day 1 (post-dose) through the end of the patient's participation will be blinded to the Sponsor and the site. An unscheduled CBC may be collected at the request of the Safety Monitor.

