- 30) The ET visits should be conducted 28 (± 3), 35 (± 3), 56 (± 3), and 84 (± 3) days after the last dose of study drug or prior to this, if necessary, to ensure compliance with the visit. If only 1 ET visit is possible, EGD and end-of-study blood work may occur on the same day (28 days after last dose and 35 days after last dose visit procedures). If the end-of-study visit occurs more than 35 days after the last dose of study drug, then perform the visit as soon as possible. The procedures listed under the 28-day and 35-day post-study drug visit will be conducted unless otherwise directed by the Medical Monitor.
- 31) The final hematology assessment for AK002-016 **must** be collected **prior to** the subject taking prednisone premedication for AK002-016X. Therefore, dosing in AK002-016X must take place at least 1 day after completion of the Day 176 visit for AK002-016. Subjects may start AK002-016X dosing 1 day after completion of the Day 176 Visit.
- 32) Blood samples for histamine and tryptase to be collected within 1–2 hours of start of symptoms if there is any suspicion of anaphylaxis.
- 33) For patients who do not start the extension study before Day 197 or Day 225, visit procedures will occur according to the AK002-016 study.

6. Criteria for Evaluation

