12.1 Screening Period

- 1) Obtain written informed consent.
- 2) Assign the participant a PID.
- 3) Begin the collection of SAE related to any screening activities.
- 4) Collect demographics and medical history.
- 5) Record prior and concomitant medications.
- 6) Determine body weight and height.
- 7) Activate patient access to ePRO questionnaire portal and instruct patient on use of the website to complete the questionnaire(s). Use the ePRO Teaching Tool to instruct the patient on use of the electronic platform ([Appendix 7](#)).
- 8) **cci** to be completed by the patient.

- 9) Perform baseline diet assessment.
- 10) Complete previous treatments review.
- 11) Obtain vital signs before blood draws and after patient at rest ≥ 5 minutes.
- 12) Perform a complete physical examination.
- 13) Obtain a 10-lead or 12-lead ECG before blood draw.
- 14) Collect the following samples for the central laboratory:
 - a) CBC with differential
 - b) Chemistry (sample to be tested for FSH and hCG if patient is of childbearing potential)
 - c) Urinalysis
 - d) Blood for serology testing (includes *Strongyloides stercoralis*)
 - e) Blood for PK
 - f) Blood for ADA
 - g) Blood for total serum IgE
- 15) Provide patient a stool collection kit and ask patient to provide a stool sample while on site or return it to the site within 1 day of collection.
- 16) Perform a screening EGD with biopsy following procedures provided by Allakos any time during the screening period.
- 17) ~~CCI~~ to be self-completed by patient on screening Day 18 (not a clinic visit).
- 18) Using results from the Central Histology Reader, confirm the eosinophil count from the gastric and/or duodenal biopsies qualify the patient for the study and no exclusionary criteria are found on the EGD.

12.2 Prior to Day 1

The following procedures will be performed prior to Day 1:

- Patient should self-administer 60 mg oral prednisone (or alternative premedication approved by the Medical Monitor) 12–24 hours prior to infusion start. Patient should remember what time they took the premedication.

12.3 Day 1 – Randomization/Infusion 1

- 1) Prior to the infusion:
 - a) Assess the patient for SAEs related to screening procedures.
 - b) Confirm continuing eligibility.
 - c) Document any changes to health status.
 - d) Document any changes to concomitant medications.
 - e) Document any changes to baseline diet.
 - f) **CCI** [REDACTED].

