 - g) Confirm **CCI** [REDACTED] was completed electronically on screening Day 18. If it was not completed have patient complete a paper version of the questionnaire.
 - h) Determine body weight.
 - i) Urine for urinalysis.
 - j) Perform urine pregnancy test (if patient is of childbearing potential).
 - k) Collect vital signs within 30 minutes of the start of the infusion.
 - l) Perform symptom-directed physical exam, if needed.
 - m) Blood for CBC with differential.
 - n) Blood for Chemistry.
- 2) Prior to randomizing the patient in the IRT system, the site will identify the highest weekly TSS of disease activity recorded during the screening period in order to stratify patients to TSS ≥ 28 or TSS < 28 and whether the patient has an EoD-only diagnosis, as identified by the screening EGD. The study coordinator or designee will enter the highest weekly TSS into the IRT on Study Day 1 to stratify the patient, as well as body weight and PID to assign kit(s).
- 3) The IRT system will then randomly assign the patient to AK002 at a dose of 1 mg/kg (first dose) or placebo in a double-blind manner and will send an email to the pharmacist and/or designee detailing the kit number(s) to use to prepare the infusion, the dose to prepare (1 mg/kg), and the patient's body weight.
- 4) The study pharmacist will prepare study drug using the weight obtained at the visit. The final combined volume of the IV bag of study drug + 0.9% NaCl will be **120 mL**.

Note: **100 mL** of the calculated dose of study drug will be administered to the patient.

The extra 20 mL is to be used to prime the IV infusion line during the preparation of the IV line at the bedside or to be left over in the infusion bag.

5) Infusion of Study Drug:

- a) Infuse 100 mL of study drug over at least 4 hours using an infusion pump. See the Pharmacy Manual for infusion rates. Record the start and stop times of the infusion including any times the infusion is interrupted.
- b) Collect vital signs 15 (± 5) minutes after the start of infusion.
- c) If anaphylaxis is suspected, a sample of blood should be obtained for plasma histamine level and tryptase within 1–2 hours of the onset of symptoms. Also, an unscheduled ADA blood sample may be obtained if an immunogenicity-related AE is suspected.

6) Post-infusion:

- a) Collect vital signs within 15 minutes of the end of the infusion.
- b) Collect CBC with differential 1 hour (± 15 minutes) after the end of the infusion.

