4.1 Terminology and Definitions

Table 2 Terminology and Definitions

Terminology	Definition
“And/Or”	Condition A “and/or” B is True when 
 • A is True and B is not evaluable (not applicable) • B is True and A is not evaluable (not applicable) • A is True and B is True when both A and B are evaluable
Baseline	Baseline for non-daily assessment (e.g., laboratory tests and CCI) is defined as the non-missing value collected most recent to and before the time of the very first dose of study drug. This includes lab test collected on Day 1 Predose as an example. Baseline Total Symptom Score (TSS) will be the average of the weekly TSS collected in the last 2 weeks prior to the first dose.
Completer for the Study	Subjects who complete at least through the Day 176 visit if continuing to the AK002-016X study or Day 225 visit if not continuing to the AK002-016X study.
Concomitant Medication	Medication collected on the Prior/Concomitant Medication CRF, with end date on/after Study Day 1. Note a Prior Medication may also be a Concomitant Medication if the start date is prior to Study Day 1 and end date is on/after Study Day 1.
Enrolled	Subject who is randomized to a treatment group.
Newly Initiated Medication	Newly initiated medication refers to any medication with a start date \geq Study Day 1
Patient-Reported Outcome	The patient-reported outcome (PRO) questionnaire evaluates 8 different symptoms with 10 daily questions for intensity and frequency: 
 • Abdominal pain intensity • Nausea intensity • Vomiting intensity • Vomiting frequency

Table 2 Terminology and Definitions cont.

Terminology	Definition
Patient-Reported Outcome cont.	
 • Diarrhea intensity • Diarrhea frequency • Fullness before finishing a meal (Early satiety) intensity • Loss of appetite intensity • Bloating intensity • Abdominal cramping intensity 
Each intensity evaluation is scored on a scale of 0=none to 10=worst possible.

Prior Medication	Medication collected on the Prior/Concomitant Medication CRF, with start date prior to Study Day 1.
PRO Total Symptom Score	Total symptom score (TSS) is the sum of 6 (abdominal pain, abdominal cramping, bloating, nausea, early satiety, and loss of appetite) weekly average symptom intensity scores.

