5.2 Visit Window and Unscheduled Assessments

Data collected for study assessments provide information on the status of the subject at a given time point. These may provide biased results if the assessment is performed early or late.

Therefore, assessments will be slotted into analysis windows to allow summaries to be performed for subjects with similar study drug exposure. The analysis window is constructed by the medians of 2 target study days of the adjacent planned visits.

Table 3 Analysis Window Rules for CCI

Visit Description	Window
Baseline	On or Prior to Day 1 Predose
Day 1	Predose on infusion Day 1
Day 29	Day 1 Postdose to Day 42
Day 57	Day 43 to Day 70
Day 85	Day 71 to Day 98
Day 113	Day 99 to Day 126
Day 141	Day 127 to Day 158
Day 176	Day 159 to Day 186
Day 197	Day 187 to End of Study

Table 4 Analysis Window Rules for Vital Sign and Laboratory Tests

Visit Description	Window
Baseline	On or Prior to Day 1 Predose
Day 1	Day 1 Postdose
Day 15	Day 2 to Day 22
Day 29	Day 23 to Day 42
Day 57	Day 43 to Day 70
Day 85	Day 71 to Day 98
Day 113	Day 99 to Day 126
Day 141	Day 127 to Day 158
Day 176	Day 159 to 186
Day 197	Day 187 to End of Study

Table 5 Analysis Window Rules for PK Concentration and ADA

Visit Description	Window
Baseline	On or Prior to Day 1 Predose
Day 8	Day 1 Postdose to Day 11
Day 15	Day 12 to Day 22
Day 29	Day 23 to Day 42
Day 57	Day 43 to Day 70
Day 85	Day 71 to Day 98
Day 113	Day 99 to Day 126
Day 141	Day 127 to Day 154
Day 169	Day 155 to Day 172
Day 176	Day 173 to Day 186
Day 197	Day 187 to Day 210
Day 225	Day 211 to End of Study

Table 6 Analysis Window Rules for Blood Histamine and Urinalysis

Visit Description	Window
Baseline	On or Prior to Day 1 Predose
Day 1	Predose on Day 1
Day 29	Day 1 Postdose to Day 42
Day 57	Day 43 to Day 70
Day 85	Day 71 to Day 98
Day 113	Day 99 to Day 126
Day 141	Day 127 to Day 158
Day 176	Day 159 to Day 186
Day 197	Day 187 to End of Study

In the event of multiple values from unscheduled or early termination assessments within a single analysis window, the value closest to the scheduled visit target study day will be used for analyses. If 2 values tie as closest to the time point (for example, 1 value is before and the other value is after the time point), then the later value will be selected. Data collected at all visits will be included in the data listings with visit presented as reported by the site.

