9.3 Appendix 3: List of Tables, Figures, and Listings

Tables

Table 14.1.1a	Subject Disposition and Reason for Discontinuation (All Screened Subjects)
Table 14.1.1b	Subject Disposition and Reason for Discontinuation (Safety/ITT Population)
Table 14.1.1c	Subject Disposition and Reason for Discontinuation (Per Protocol Population)
Table 14.1.2	Major Protocol Deviations During the Study: Subject Count (All Randomized Subjects)
Table 14.1.3	Analysis Population: Subject Count (All Randomized Subjects)
Table 14.1.4	Per Protocol Population Exclusion (All Randomized Subjects)
Table 14.1.5a	Demographics and Baseline Characteristics (Safety/ITT Population)
Table 14.1.5b	Demographics and Baseline Characteristics (Per Protocol Population)
Table 14.1.6	Medical History by System Organ Class and Preferred Term: Subject Incidence (Safety Population)
Table 14.1.7.1	Study Drug Exposure (Safety Population)
Table 14.1.7.2	Study Drug Exposure (Safety Population)
Table 14.1.7.3	Duration of Treatment Exposure and Compliance (Safety Population)
Table 14.1.8.1	Prior Medications by Anatomic Therapeutic Chemical Classification and Preferred Term: Subject Incidence (Safety Population)
Table 14.1.8.2	Concomitant Medications by Anatomic Therapeutic Chemical Classification and Preferred Term: Subject Incidence (Safety Population)
Table 14.1.9	Severity of Concomitant Asthma and Atopic Dermatitis at Baseline (ITT Population)
Table 14.1.10	12-Lead ECG Evaluation at Baseline (Safety Population)
Table 14.1.11	Baseline Eosinophil and CCI (ITT Population)
Table 14.1.12	Baseline Worst Dysphagia Severity Score (ITT Population)

Table 14.1.13	Baseline Subject Reported Outcome Total and Symptom Scores (MITT Population)
Table 14.1.14	Baseline Vital Signs (MITT Population)
Table 14.1.15	Subject Incidence of Intercurrent Events (MITT Population)
Table 14.2.1.1	Tissue Eosinophil Responder at Week 24 – Primary and Sensitivity Analysis (MITT Population)
Table 14.2.1.2.1	Tissue Eosinophil Responder at Week 24 by Disease Subgroup (MITT Population)
Table 14.2.1.2.2	Tissue Eosinophil Responder at Week 24 by Gender (MITT Population)
Table 14.2.1.2.3	Tissue Eosinophil Responder at Week 24 by Age Subgroup (MITT Population)
Table 14.2.1.2.4	Tissue Eosinophil Responder at Week 24 by Baseline Peripheral Eosinophil Count Subgroup (MITT Population)

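### The haematology baseline is a Day 1 sample drawn after the prednisone premedication, so blood-eosinophil changes, shifts and any absolute-cut subgroup start from a premedicated value

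*SAP*

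**What the plan says.** SAP 4.1, Table 2: for assessments that are not daily, baseline "is defined as the non-missing value collected most recent to and before the time of the very first dose of study drug", and the entry continues "This includes lab test collected on Day 1 Predose as an example". SAP 5.2, Table 4, gives the laboratory baseline window as "On or Prior to Day 1 Predose". The Day 1 row of that table holds post-dose values only, so the Day 1 predose count has no row except as baseline.

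Protocol Table 1 note 19: "Premedication with 60 mg oral prednisone or approved alternative is required 12–24 hours prior to first infusion". Protocol 12.2 repeats it as an instruction: "Patient should self-administer 60 mg oral prednisone". Protocol 12.3 then lists "Blood for CBC with differential" among the Day 1 steps before the infusion. A count is also taken at screening (Protocol 11.2.5), but under Table 2 it becomes baseline only if the Day 1 predose value is missing.

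Protocol Table 1 note 31 requires the last haematology sample of this study to come before "the subject taking prednisone premedication for AK002-016X".

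The laboratory baseline feeds haematology Tables 14.3.2.1 (change) and 14.3.2.3 (shift), and SAP 6.5 lists a baseline descriptor of at least 500 blood eosinophils/µL. SAP Appendix 3 also plans Table 14.2.1.2.4, "Tissue Eosinophil Responder at Week 24 by Baseline Peripheral Eosinophil Count Subgroup (MITT Population"), and a matching Table 14.2.2.5.4 for the symptom score.

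**The concern.** The two ends of the haematology comparison are taken under different conditions. Baseline follows a large single steroid dose by 12–24 hours. Later samples are normally unpremedicated, because premedication after Day 1 needs written Medical Monitor approval. Note 31 shows that the sponsor regards prednisone as able to disturb a haematology result.

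Depletion of blood eosinophils is the drug's stated pharmacology, so this is the laboratory measure readers will look at first. If prednisone lowers the count:

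- placebo patients will appear to rise after Day 1;
- the fall on AK002 will look smaller than it is;
- a patient whose usual count is above normal may start a shift table in the normal category;
- any grouping by a fixed baseline count will put some patients in the lower group because of the premedication.

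**Working it through.** **Plan's own figures.** The documents state no figure for this point. Power for the symptom endpoint does not depend on a blood count. It reproduces at 96.3% by the normal approximation (80 per group, difference 7.4, SD 12.5, two-sided 0.05) against the stated 96%, and nothing below changes it.

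**Order of events for infusion 1.** Screening count → prednisone or approved alternative at −24 to −12 h → Day 1 predose count, which is the SAP baseline → infusion → one-hour post-infusion count. The documents fix this order; it is not an assumption.

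**Size.** Let *r* be the fraction by which premedication lowers the eosinophil count at 12–24 h. The documents do not give *r*. The range 0.2–0.8 is assumed for illustration and taken as the same for all patients. With an unpremedicated count *C*, the recorded baseline is (1 − r)C.

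- Unchanged placebo patient, apparent percent change: [C − (1 − r)C] / [(1 − r)C] = r/(1 − r).
- AK002 patient with a true 95% fall to 0.05C, apparent percent change: 0.05/(1 − r) − 1.
- Unpremedicated count needed to be recorded as at least 500: 500/(1 − r).

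| r (assumed) | Unchanged placebo | True −95% on AK002 | Count needed to be classed ≥500/µL |
|---|---|---|---|
| 0 | 0% | −95.0% | 500 |
| 0.2 | +25% | −93.8% | 625 |
| 0.4 | +67% | −91.7% | 833 |
| 0.6 | +150% | −87.5% | 1250 |
| 0.8 | +400% | −75.0% | 2500 |

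For example, take C = 800 cells/µL and r = 0.4. The baseline is 0.6 × 800 = 480, which is already below 500. An unchanged placebo patient records 800 − 480 = +320. An AK002 patient who truly falls to 40 records 40 − 480 = −440, not −760.

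**What is preserved.** Both arms are premedicated, so the baseline term cancels in the difference in absolute change: [40 − 800(1 − r)] − [800 − 800(1 − r)] = 40 − 800 = −760 for every *r*. Check at r = 0.4: −440 − 320 = −760.

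**Which outputs use this baseline.**

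- Tables 14.3.2.1 and 14.3.2.3 use it directly. SAP 6.15.2 plans change from baseline, not percent change, but any percentage read from those tables carries the distortion.
- The 500 cells/µL descriptor in SAP 6.5 uses it, for a subject listing.
- Tables 14.2.1.2.4 and 14.2.2.5.4 depend on their cut-point. None is stated, and blood eosinophils are absent from the subgroup list in SAP 5.9. An absolute cut shifts as in the last column. A median split would not, under a constant *r*, because ranks are unchanged.
- The tissue-eosinophil baseline comes from the screening endoscopy, and the symptom baseline is the average of two weekly scores. Neither uses the Day 1 blood count.

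**The case against.** The last value before first dose is a usual convention, and the effect here is confined to descriptive output. Protocol section 15 says that no formal inference will be made on safety parameters. SAP 6.15.2 shows actual values beside changes at each visit, so absolute counts on AK002 can be read against concurrent placebo and depletion is not hidden. The size and direction of the steroid effect come from an assumption. All of this stands. It limits the consequence but does not justify a haematology baseline that the sponsor's own note 31 would not accept for the final sample.

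A reader might go further in four ways that the documents do not support.

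- **The co-primary results are biased.** They use no blood count. Even in the eosinophil subgroup tables both arms are premedicated, so the within-subgroup comparison stays fair; only who belongs to the subgroup changes.
- **The subgroup tables certainly misclassify patients.** No cut-point is given, and the 500 figure appears only in SAP 6.5.
- **The whole chemistry panel should move to screening.** Note 31 concerns haematology only. A same-day predose reference for liver enzymes or creatinine may be better than one several weeks old.
- **Screening is steroid-free.** Protocol 8.2 allows stable corticosteroids up to 10 mg/day of prednisone or equivalent, so screening is free of premedication but not necessarily of steroid. Nor does every patient necessarily take prednisone, since an approved alternative is allowed.

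**Conclusion.** The concern holds for the blood count with differential. The sampling order and the baseline rule are explicit in the documents, and the contrast with note 31 is internal to the protocol.

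Under an assumed common suppression of 20–80%, an unchanged placebo patient shows +25% to +400%, a true 95% fall shows as −93.8% to −75.0%, and true counts from 500 up to 625–2500 cells/µL are classed below 500. These figures are for eosinophils only; the documents support no figure for other cell types. The result bears on within-arm changes and shifts in Tables 14.3.2.1 and 14.3.2.3, the SAP 6.5 descriptor and, only if an absolute cut is used, Tables 14.2.1.2.4 and 14.2.2.5.4.

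Power, sample size, the co-primary tests and the between-arm difference in mean absolute change are untouched. Several exploratory endpoints are blacked out, so no conclusion is drawn about them.

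**What to change.** In SAP Table 2 and Table 4, for the blood count with differential only:

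- Define baseline as the last non-missing value before the Day 1 premedication, normally the screening sample. Describe it as free of premedication, not as steroid-free.
- Use it for Tables 14.3.2.1 and 14.3.2.3, the 500 cells/µL descriptor in SAP 6.5, and Tables 14.2.1.2.4 and 14.2.2.5.4. State the cut-point for those two subgroup tables, and add the subgroup to SAP 5.9.
- Give Day 1 predose its own row, and keep it as the reference for the Day 1 one-hour post-infusion sample.

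Leave the chemistry baseline at Day 1 predose. At most, add a supportive display of glucose against screening.

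The cost is SAP wording and one derivation flag, settled before the provisional database lock. No new data are needed, and no dose or clinical rule changes. The downside is age: the screening sample may be up to about 45 days old, and older where bloods from AK002-014 screening are reused (Protocol 11.5.11). Showing the Day 1 predose row beside it lets readers see how much the choice matters.
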